steering committee members before execution, with reasons provided. If the trial steering committee deems the reason valid, the order to advance or delay the catheter removal is allowed to be executed; 4) Nurses need to educate and guide enrolled patients to ensure that patients in the bladder training group actively perform forceful urination during each period of unclamping to assist in urine discharge; 5) Patients in the bladder training group, if unable to persist in reaching the specified catheter clamping time (less than 3 hours of catheter clamping before feeling the urge to urinate), may end a training cycle early, open the catheter for 5 minutes, and then start the next clamping training cycle; 6) Before catheter removal, patients in the bladder training group must complete the Bladder Training Quality Self-Assessment Form; 7) During the first catheterization of the patient, selective α 1-adrenergic receptor blockers (such as Tamsulosin) should not be used. If it is necessary to use them due to the patient's condition, the reasons should be recorded; 8) Each patient enrolled in the study will be given a subject compensation of 100 yuan to increase the compliance of the enrolled patients and the success rate of follow-up.

(3) Endpoint quality control

Our project team requires all levels of physicians in our department to strictly follow the bladder residual urine assessment method and the criteria for secondary catheterization as stipulated in the project research plan to calculate bladder residual urine and decide whether to perform secondary catheterization. To reduce bias in the measurement of bladder residual urine, this study implements quality control in the following two aspects: 1) A fixed radiologist is responsible for assessing bladder residual urine, and this physician has specialized in abdominal digestive and urinary system ultrasound examinations for over 10 years; 2) The ultrasound diagnosis location is set in the same therapeutic area as the patient, ensuring that patients can undergo immediate ultrasound examination after the first urination following catheter removal, avoiding the impact on the judgment of residual urine due to a long interval between urination and ultrasound examination; 3) For patients who fail to undergo the residual urine volume assessment in a timely manner for various reasons after the first urination, a bladder ultrasound should be conducted immediately after the second

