6.3 Missing data and its handling approaches

6.3.1 Definition of Missing Data

Since the primary endpoint is a composite endpoint, if a patient fails to achieve any of the positive events within the primary endpoint (secondary catheterization or residual urine volume > 100 ml) and any of the following situations occurs: 1) the residual urine volume after the first urination following the removal of the urinary catheter is missing; or 2) the situation of secondary catheterization within 7 days after the removal of the urinary catheter is missing, the primary endpoint will be defined as missing. The possible reasons for the missing primary endpoint include: 1) loss to follow - up or death, making it impossible to know whether secondary catheterization occurs within 7 days after the removal of the urinary catheter; 2) after the removal of the urinary catheter, due to various reasons, the bladder ultrasound for assessing the residual urine volume after the first urination is not carried out in a timely manner; 3) the patient refuses the researcher to use the data related to the patient's own micturition function.

In the case where a subject refuses the researcher to use their personal data, that

is, the subject requests to withdraw the informed consent and drop out of this study midway, all the data of this patient will be treated as missing data in the ITT analysis. If the subject refuses the collection of research data after withdrawal but consents to the collection of data before withdrawal, the researcher will treat the data after withdrawal as missing values, and the data before withdrawal can be included in the analysis.

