6.3.2 Methods for handling missing data

In this study, if the missing rate of the primary endpoint is less than 5%, no imputation of missing data will be done in the analysis of the primary endpoint in the ITT, PPA, and ATA sets. During the analysis of the primary outcome, missing data will be treated as censored.

If the missing rate of the primary endpoint is 5% or higher at the end of the study, the following procedures will be adopted to handle the data with missing values in any variable of the primary endpoint.

- 1) When the data on post-void residual urine volume (RUVR) by ultrasound after the first urination is complete, and the situation of secondary catheterization within 7 days after the removal of the urinary catheter is also complete. There is no missing data.
- 2) When the data on post-void RUVR by ultrasound after the first urination is complete, but the situation of secondary catheterization within 7 days after the removal of the urinary catheter is missing.

If the post-void RUVR by ultrasound after the first urination is greater than 100 ml, handling method: The primary endpoint is reached (positive), and no imputation of missing data for secondary catheterization is performed.

If the post-void RUVR by ultrasound after the first urination is less than or equal to 100 ml, handling method: Multiple imputation method is used to impute the missing data of secondary catheterization.

3) When the data on post-void RUV by ultrasound after the first urination is missing, but the situation of secondary catheterization within 7 days after the removal of the urinary catheter is complete.

If secondary catheterization occurs within 7 days after the removal of the urinary catheter, handling method: The primary endpoint is reached (positive), and no imputation of missing data for RUV is performed.

If secondary catheterization does not occur within 7 days after the removal of the urinary catheter, and the post-void RUV by ultrasound after the second urination is not missing, handling method: The Last Observation Carried Forward (LOCF) method is used to impute the missing data of the first residual urine volume. In LOCF method, the post-void RUV after the second urination is used to impute missing data of the first post-void RUV.

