If secondary catheterization does not occur within 7 days after the removal of the urinary catheter, and the post-void RUV by ultrasound after the second urination is also missing, handling method: Multiple imputation method is used to impute the missing data of the first post-void RUV.

4) When the data on post-void RUV by ultrasound after the first urination is missing, and the situation of secondary catheterization within 7 days after the removal of the urinary catheter is also missing.

If the post-void RUV by ultrasound after the second urination is not missing, handling method: The LOCF method is used to impute the missing data of the first residual urine volume. If the imputed residual urine volume is greater than 100 ml, the primary endpoint is reached (positive), and no imputation of missing data for secondary catheterization is performed; if the imputed residual urine volume is less than or equal to 100 ml, multiple imputation method is used to impute the missing data of secondary catheterization.

If the post-void RUV by ultrasound after the second urination is also missing,

handling method: Multiple imputation method is used to impute the missing data of the primary endpoint. At this time, the primary endpoint is imputed as a whole missing data, rather than imputing the RUV and secondary catheterization separately.

Through the above treatment methods, we will minimize the impact of missing data on the research results and ensure the accuracy and reliability of data analysis. The handling process of missing data in primary endpoint is shown in Figure 1.

In the analysis of secondary endpoint and subgroup analysis, we will not perform imputation of missing data.

Handling flow of missing data for primary endpoint

Both the RUV after the patient's first urination and the secondary catheterization data within 7 days after catheter removal are complete

No missing data, no processing required

The RUV after the patient's first urination is complete but the secondary catheterization data within 7 days after catheter removal is missing

The RUV after the first urination is >100 ml

The primary endpoint is achieved, and no imputation for missing data on secondary catheterization is required

The RUV after the first urination is ≤100ml

Multiple imputation method is employed to handle the missing data for secondary catheterization

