6.5.4 Subgroup analysis

We will explore differences in the primary endpoint between the two groups in different subgroups through subgroup analysis. Logistic regression will be used for univariate and multivariate analyses, with effect sizes represented by OR and 95% CI, and interaction P-values will be calculated. The subgroups include:

- Sex: male, female
- Age: ≤ 65 years, > 65 years
- Tumor site: the lower edge of the tumor is above the peritoneal reflection; the lower edge of the tumor is below or at the peritoneal reflection
- Other variables independently associated with primary endpoints in multivariate analysis.

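### At 5% or more missing primary endpoints, patients whose outcome is filled in for the ITT analysis are left out of the subgroup models of the same endpoint

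*SAP*

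**What the plan says.** SAP 6.3.1 counts a patient as missing only if neither positive component was observed and either the first-void residual or the 7-day catheterisation status is unknown; in that case "the primary endpoint will be defined as missing".

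SAP 6.3.2 then sets two regimes.

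- Below the threshold: "if the missing rate of the primary endpoint is less than 5%, no imputation of missing data will be done". This covers the ITT, per-protocol and as-treated sets.
- At or above it: "If the missing rate of the primary endpoint is 5% or higher at the end of the study, the following procedures will be adopted". A second-void scan, where there is one, replaces the missed first-void scan: "In LOCF method, the post-void RUV after the second urination is used to impute missing data of the first post-void RUV". Remaining gaps are multiply imputed. SAP 6.5.2.1 applies this scheme in the ITT set.

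The same section closes with "In the analysis of secondary endpoint and subgroup analysis, we will not perform imputation of missing data". Protocol version 2.0, section 11.3.2, carries the same sentence.

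SAP 6.5.4 makes the primary endpoint the subgroup outcome: "We will explore differences in the primary endpoint between the two groups in different subgroups through subgroup analysis". It uses logistic regression and reports odds ratios and interaction P values. It names no analysis set. The sensitivity analyses for missing data in SAP 6.5.2 are for the ITT comparison, and none is planned for the subgroups.

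**The concern.** Once the 5% rule is triggered, one endpoint is analysed on two sets of patients. The overall comparison uses everyone randomised. The subgroup models use only patients whose endpoint was observed, because a logistic model without imputation omits anyone with no outcome. That omission is inferred from the no-imputation rule; the documents do not spell it out.

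The subset is not a neutral one. Among patients whose first-void scan was missed, SAP 6.3.1 and 6.3.2 keep those who were re-catheterised, as events, and treat those who were not as missing. The subgroup models therefore retain known events and lose patients with a lower expected event rate. If missed scans are more common in one arm, sex, age band or tumour site, the subgroup odds ratios and interaction P values could move for reasons unrelated to the intervention.

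The branch may well be reached. The plan allows for 10% dropout, twice the trigger, although dropout and missing endpoints need not coincide.

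**Working it through.** **Inputs from the documents.** Event rates 44.7% (ICCAUT) and 59.3% (free drainage), 200 per arm, 10% dropout (protocol 11.1, SAP 5); 5% trigger (SAP 6.3.2).

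**The plan's own figure.** With two-sided α = 0.05, 80% power and unpooled variance:

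n = (1.960 + 0.842)² × (0.447×0.553 + 0.593×0.407) / 0.146² = 179.9, so 180 per arm, and 180/0.9 = 200. The figure reproduces. (SAP 5 calls this α one-sided, which would give 142; that is a separate matter.)

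**Scale.** The planned difference, control minus ICCAUT, is 14.6 points, with OR 0.555. Its standard error is √[(0.447×0.553 + 0.593×0.407)/200] = 4.94 points. At 5% missing, 20 of 400 patients are affected, so ITT uses 400 and the subgroup models 380. At 10% it is 400 against 360.

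**Check 1: following the missing-data rule.** Assume that a fraction m of first-void scans is missed independently of outcome, that a fraction c of each arm is re-catheterised, that no second-void scan is used, and that ITT imputation recovers the full-data rates. In an arm with event rate p:

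- fraction left out = m(1 − c)
- event rate among those left out = (p − c)/(1 − c)
- event rate among those kept = [p − m(p − c)] / [1 − m(1 − c)]

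At c = 10%, those left out have event rates of 38.6% (ICCAUT) and 54.8% (control). At c = 20% the rates are 30.9% and 49.1%. All four are below the arm's own rate.

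| Missed scans, ICCAUT / control | c | Left out, of 400 | Kept-patient rates | Difference | Shift |
|---|---|---|---|---|---|
| 10% / 10% | 10% | 36 | 45.3% / 59.7% | 14.4 | −0.2 |
| 10% / 10% | 20% | 32 | 45.9% / 60.2% | 14.3 | −0.3 |
| 5% / 15% | 10% | 36 | 45.0% / 60.0% | 15.0 | +0.4 |
| 5% / 15% | 20% | 32 | 45.3% / 60.7% | 15.4 | +0.8 |
| 15% / 5% | 10% | 36 | 45.7% / 59.5% | 13.9 | −0.7 |
| 15% / 5% | 20% | 32 | 46.6% / 59.7% | 13.1 | −1.5 |

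The entries are rounded from unrounded values. Every row is above the 5% trigger (32/400 = 8%, 36/400 = 9%). The largest shift, 1.46 points before rounding, is 0.3 SE.

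**Check 2: a wider range.** Remove k patients per arm with a common event rate r; the remaining rate is (200p − kr)/(200 − k). The splits and rates are assumptions.

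| k, ICCAUT / control | Shift at r = 30% | Shift at r = 50% | Shift at r = 70% |
|---|---|---|---|
| 8 / 16 | +1.9 | +1.0 | +0.1 |
| 16 / 8 | −0.1 | +0.9 | +1.8 |
| 12 / 28 | +3.8 | +1.9 | −0.1 |
| 28 / 12 | −0.5 | +1.5 | +3.4 |

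Worked example, 12/28 at 30%: (89.4 − 3.6)/188 = 45.6% and (118.6 − 8.4)/172 = 64.1%. The difference is 18.4 points and the OR 0.47. Over the grid the shift runs from −0.5 to +3.8 points (−0.1 to +0.8 SE). If the removed patients have exactly their own arm's rate, there is no shift, only lost precision.

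Both checks describe the whole trial. Neither is an estimate of bias in a subgroup effect or an interaction.

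**The case against.** The strongest defence is that this is a declared choice. Protocol and SAP give the same rule, in advance, for analyses described as exploratory. Complete-case analysis is common in that setting, and with only the outcome missing it is valid when missingness depends only on covariates in the model. That condition fails here, because the definition of missing makes exclusion depend on whether the patient was re-catheterised, which is part of the outcome. The rest stands: the two documents agree with each other, the rule is open, and the primary result is untouched.

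Other points also stand.

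- Subgroup results are odds ratios and the ITT result is a risk difference, so they would not average to one another even with identical data.
- Imputation brings its own risk: an imputation model without arm-by-subgroup terms pulls interactions towards zero, and the SAP specifies no imputation model.
- The subgroup analysis set is unnamed, and extra subgroup variables come from a per-protocol multivariate model (SAP 6.5.1). If subgroups were run per protocol, denominators would differ anyway.
- The protocol takes steps to limit missing endpoints, such as duty-physician scans after 18:00 and second-void scans (version 2.0, section 10 (3)), so the branch may never be used.

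A reader might infer that the same patient receives conflicting scores in the two analyses. The documents do not support that: affected patients are scored in ITT and unscored in the subgroups, and everyone else is scored identically.

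A reader might also extend the point to the regime below 5%, where second-void scans go unused. There ITT and subgroups agree. Whether to use those scans is a separate trade-off, because the emptying component of the endpoint is defined on the first void.

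**Conclusion.** The point holds as a cheap improvement. At 5% or more missing, and only then, the subgroup models rest on a smaller, outcome-selected part of the patients behind the ITT result, and neither document says why.

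The expected size is small: about 0.2–0.3 points on a 14.6-point difference if scans are missed at random in 10% of both arms, and about 0.4–1.5 points if 5% are missed in one arm and 15% in the other, assuming 10–20% re-catheterisation. The wider grid of assumed splits and event rates gives −0.5 to +3.8 points, at most 0.8 SE. All these figures rest on the planning rates and on assumed missingness, and treat the completed ITT data as correct.

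It would be tempting to conclude that the plan will produce false subgroup interactions. The documents do not support that: a spurious interaction is possible in principle, but its size depends on missingness by arm within subgroup, which they do not give.

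**What to change.** In SAP 6.3.2 and protocol 11.3.2, strike the reference to subgroup analysis from the no-imputation sentence. Then state that, when the 5% rule triggers imputation:

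- subgroup and interaction models of the primary endpoint use the same scored and imputed ITT data as the primary analysis, pooled by Rubin's rules;
- the imputation model includes arm, the subgroup variables and arm-by-subgroup terms;
- complete-case subgroup results are given as a supplement.

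This also settles which analysis set the subgroups use. The 5% trigger and the handling below it stay as they are.

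The cost is a change of wording in two documents and slightly more analysis work; no new data are needed. The downside is that subgroup results then depend on the imputation model, and the complete-case supplement lets a reader see how much.

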6.4 Characteristics of the population

The following baseline characteristics will be presented in ITT, Per-protocol (PP) and as-treated (AT) population.

6.4.1 Preoperative characteristics

- Sex, categorical variable: male, female;
- Age, continuous variable, measured in years;
- Body Mass Index, continuous variable, measured in kg/m²;
- American Society of Anesthesiologists grading, categorical variable: I, II, III, IV;
- Neoadjuvant radiotherapy/chemoradiotherapy, categorical variable: no, yes;
- Tumor site, categorical variable: the lower edge of the tumor is above the peritoneal reflection, the lower edge of the tumor is not above (below or at) the peritoneal reflection.
- The distance from the lower edge of the tumor to the anal margin, continuous variable, measured in centimeter;
- Benign prostatic hyperplasia, categorical variable: No, Yes;
- History of hypertension, categorical variable: No, Yes;
- History of diabetes, categorical variable: No, Yes;
- ICIQ-SF score at admission, continuous variable, measured in points;
- ICIQ-SF classification at admission, categorical variable: no or mild, moderate, severe;
- IPSS score at admission, continuous variable, measured in points;
- IPSS classification at admission, categorical variable: mild, moderate, severe;
- Clinical T stage, categorical variable: clinical complete response (cCR), T1, T2, T3, T4;
- Clinical N stage, categorical variable: N0, N1, N2;
- Clinical TNM stage, categorical variable: 0 stage, I stage, II stage, III stage, IV stage.

6.4.2 Operative characteristics

- Surgical techniques, categorical variable: laparoscopic-assisted surgery, robotic-

assisted surgery;

- Surgical procedure, categorical variable: low anterior resection (LAR), abdominoperineal resection (APR). Subtypes of LAR include LAR with prophylactic enterostomy, LAR with intersphincteric resection (ISR), LAR with Turnbull-Cutait Pull-Through Coloanal Anastomosis (TCA), LAR with transanal total mesorectal excision (TaTME). There is overlap among different subtypes of LAR.
- Operation time, continuous variable, measured in minutes;
- Anastomosis, categorical variable: no anastomosis, colorectal anastomosis, coloanal anastomosis;
- Intraoperative blood loss volume, continuous variable, measured in milliliters;
- Intraoperative urine output volume, continuous variable, measured in milliliters;
- Intraoperative intravenous infusion volume, continuous variable, measured in milliliters;

6.5 Analysis of endpoints

6.5.1 Analysis of the primary endpoint

Categorical variables will be statistically analyzed and described using counts (percentages). Without multivariate adjustment, the primary endpoints of the two groups will be compared respectively in the ITT analysis set, the PPA set, and the ATA set. The differences between the two groups will be described using the absolute risk differences (ARD) and their 95% Confidence Intervals (95% CI). The 95% CI will be compared with an absolute risk difference of 0.

The positive primary endpoint consists of bladder residual urine volume (RUV) $>100\text{ml}$ after the first voiding or secondary catheterization within 7 days after the catheter removal. These two subtypes will also be compared between the two groups and their 95% confidence interval will be presented. Also, secondary catheterization for reasons other than urinary retention will be listed in the subsets of secondary catheterization.

Primary endpoint:

Dataset: ITT, PPA and ATA				
Variables	Free-drainage group N=***	ICCAUT group N=***	Absolute risk difference (95% CI)	P value
Urinary dysfunction	** (**)	** (**)	** (** to **)	*.***
RUV >100ml	** (**)	** (**)	** (** to **)	-
Secondary catheterization	** (**)	** (**)	** (** to **)	-
Urinary retention	** (**)	** (**)	** (** to **)	-
Not urinary retention (notes on the specific reasons)	** (**)	** (**)	** (** to **)	-
Missing data	** (**)	** (**)		

In addition, in the PPA set, the Chi-square test or Fisher's exact test will be used to analyze the variables related to the primary endpoint. Multivariate logistic regression will be employed to adjust the factors that may have an impact on the primary endpoint, and to analyze the independent risk factors affecting the primary endpoint. During this process, continuous variables will be transformed into categorical variables. The variables used for adjustment include the patient grouping in the PPA dataset (ICCAUT group/free-drainage group), tumor site (the lower edge of the tumor is above the peritoneal reflection/the lower edge of the tumor is below the peritoneal reflection), sex (male/female), and age (≤ 65 years old/ > 65 years old). In addition to the above variables, variables with a p-value < 0.1 in the univariate analysis will also be included. After adjustment, the differences between the groups will be described using the Odds Ratio (OR) and 95% CI.

Univariate analysis:

Dataset: PPA	
17 Mar 2025	SAP version 1.0

Variables	Without Urinary dysfunction N=***	With Urinary dysfunction N=***	P value
Interventions			*.***
Free drainage	**(**)	**(**)	
ICCAUT	**(**)	**(**)	
Sex			*.***
Male	**(**)	**(**)	
Female	**(**)	**(**)	
Age			*.***
≤ 65 years old	**(**)	**(**)	
> 65 years old	**(**)	**(**)	
BMI			*.***
<24 kg/m^2	**(**)	**(**)	
≥24 kg/m^2	**(**)	**(**)	
ASA			*.***
I-II	**(**)	**(**)	
III-IV	**(**)	**(**)	
Neoadjuvant radiotherapy or chemoradiotherapy			*.***
No	**(**)	**(**)	
Yes	**(**)	**(**)	
Tumor site			*.***
Above the peritoneal reflection	**(**)	**(**)	
Below or at the peritoneal reflection	**(**)	**(**)	
Distance from the anal verge to the tumor			*.***
≤5 cm	**(**)	**(**)	
>5 cm	**(**)	**(**)	
Benign prostatic hyperplasia			*.***
No	**(**)	**(**)	
Yes	**(**)	**(**)	
IPSS classification at admission			*.***
Mild	**(**)	**(**)	
Moderate	**(**)	**(**)	
Severe	**(**)	**(**)	
ICIQ-SF classification at admission			*.***
No or mild	**(**)	**(**)	
Moderate	**(**)	**(**)	

Severe	**(**)	**(**)	
History of hypertension			*.***
No	**(**)	**(**)	
Yes	**(**)	**(**)	
History of Diabetes			*.***
No	**(**)	**(**)	
Yes	**(**)	**(**)	
Pathological stage T			*.***
pCR to T2	**(**)	**(**)	
T3 to T4	**(**)	**(**)	
Pathological stage N			*.***
N0	**(**)	**(**)	
N1 to N2	**(**)	**(**)	
Pathological stage TNM			*.***
0 to II	**(**)	**(**)	
III to IV	**(**)	**(**)	
Surgical techniques			*.***
Laparoscopic-assisted surgery	**(**)	**(**)	
Robotic-assisted surgery	**(**)	**(**)	
Surgical procedure			*.***
LAR	**(**)	**(**)	
APR	**(**)	**(**)	
Operation time			*.***
≤180 minutes	**(**)	**(**)	
>180 minutes	**(**)	**(**)	
Anastomosis			*.***
No anastomosis	**(**)	**(**)	
Colorectal anastomosis	**(**)	**(**)	
Coloanal anastomosis	**(**)	**(**)	
Intraoperative urine output volume			*.***
≤500 ml	**(**)	**(**)	
>500 ml	**(**)	**(**)	
Intraoperative intravenous infusion volume			*.***
≤1500 ml	**(**)	**(**)	
>1500 ml	**(**)	**(**)	
Duration of the indwelling urethral catheter			*.***

≤2 days	**(**)	**(**)	
>2 days	**(**)	**(**)	
Urinary tract infections			*.***
No	**(**)	**(**)	
Yes	**(**)	**(**)	

Multivariate analysis:

Dataset: PPA				
Variables	Without Urinary dysfunction N=***	With Urinary dysfunction N=***	Adjusted OR (95% CI)	P value
Interventions				*.***
Free drainage	**(**)	**(**)		
ICCAUT	**(**)	**(**)	** (** to **)	
Sex				*.***
Male	**(**)	**(**)	** (** to **)	
Female	**(**)	**(**)		
Age				*.***
≤ 65 years old	**(**)	**(**)		
> 65 years old	**(**)	**(**)	** (** to **)	
Tumor site				*.***
Above the peritoneal reflection	**(**)	**(**)		
Below or at the peritoneal reflection	**(**)	**(**)	** (** to **)	
Other variables with p value <0.1 in univariate analysis	**(**)	**(**)	** (** to **)	*.***

6.5.2 Sensitivity analysis of primary endpoints.

This study will conduct sensitivity analyses on the missing data of the primary endpoints and positive events of the primary endpoints caused by reasons other than urinary retention. The sensitivity analyses of the two situations above will be conducted in the ITT analysis set.

